4.7 Eligible eye

Assuming that all the inclusion/exclusion criteria are met in both eyes, the worse eye (eligible eye) will be determined at the baseline visit using a stepladder approach, as follows:

1. Schirmer’s Test: worse eye determined as eye with lower Schirmer I score.
2. NEI score: if Schirmer I score is the same in both eyes, worse eye will be determined by NEI score (cornea + conjunctival staining).

If all the above are identical, determination of the worse eye will be based on the investigator’s judgement, otherwise the right eye will be used as the eligible eye.

5. Sample size justification

The sample size of the study is calculated based on results from previous studies.

Sample size was calculated according to the following assumptions:

- randomization ratio 1:1.
- a difference of 30% in Schirmer I rate of responders (value >10mm/5min at week 4.) in favor of rhNGF treatment at Week 4, with a responder rate of 5% for vehicle.
- 15 points in Global SANDE score improvement at Week 12, with a standard deviation of 20 points.

Based on these assumptions, a total sample size of 90 evaluable patients (100 pts considering 10% of patients not evaluable after enrollment) allows to achieve an overall power of 90% to show superiority of rhNGF eye drops solution vs vehicle in terms of both co-primary endpoints, considering a one-sided alpha of 0.025. Specifically:

- A power of 95.8% is achieved for Schirmer I primary endpoint.
- A power of 94.0% is achieved for SANDE primary endpoint.

6. Randomization and blinding

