10.1.3 Sensitivity analyses

The following sensitivity analyses are defined to assess the robustness of results on each primary endpoint versus assumptions used in the statistical model for the main estimators:

- The comparison between treatment and control will be performed by means of MI under MAR assumption instead of MNAR. MI will be implemented in two steps:
 - Intermittent missing data up to primary time point (Week 4 for Schirmer I test, and Week 12 for SANDE) will be imputed using MCMC methods assuming MAR. A separate imputation model will be used for each treatment arm. The imputation models will include the observed values (baseline and intermediate), gender, and age class as covariates. In case of non-convergence or non-estimability issues, a single model will be considered with treatment arm added as explanatory variable to the model.
 - The remaining missing values with a monotone missing data pattern will be imputed based on data of corresponding treatment group.
 - Each imputed dataset will be analyzed using observed and imputed data. Rubin's rule will be used for combining results to draw inference. The adjusted estimated treatment differences between cenegeerin and vehicle (difference in proportions for Schirmer's test and differences in means for SANDE) will be displayed together with the corresponding two-side 95% confidence intervals and p-values.
- A tipping point strategy will be used as a sensitivity analysis for missing data for assessment of superiority (if shown) of rhNGF for each endpoint. Tipping point analysis will assess how departures from MI under MNAR assumptions must be to overturn conclusions from the primary superiority analysis. Tipping point will be based on iterative application of MI. In the first iteration, MI-RD method is assumed as described in section 10.1.2. In successive iterations, the imputed values for the rhNGF arm are shifted by a constant to represent a worse effect in each iteration. This can be achieved by using the N completed datasets obtained under MI-RD and shift the imputed values. The tipping point is the shift at which the p-value becomes non-significant. Outline of tipping point:
 - Use MI-RD to impute missing values.
 - Assuming that the tipping point is between -10 and 0, the following actions will be performed for $\Delta = 0, -0.1, -0.2, -0.3, \dots, -10$:
 - Add Δ to the imputed values at the rhNGF arm.
 - Analyze the completed data sets using the same method outlined in section 10.1.2.

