 - the plot of all p-values for Δ between -10 and 0 will be created.
 - based on the plot, the approximate value of the tipping point $T_{p\text{approx}}$ is identified considering a threshold for the p-values of 0.02500.
 - after identification of $T_{p\text{approx}}$, finest research of the tipping point will be performed in the range $T_{p\text{approx}} \pm 1$ by incrementing Δ of 0.01 and following the usual steps:
 - Add Δ to the imputed values at the rhNGF arm.
 - Analyze the completed data sets using the same method outlined in section 10.1.2.
 - The tipping point is the smallest Δ at which $p\text{-value} \geq 0.02500$.

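### The single 10-unit tipping-point grid is too short for SANDE: under the plan's own assumptions it will rarely find a tipping point, and the SAP has no rule for that case

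*SAP*

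**What the plan says.** SAP 10.1.3 describes the tipping-point analysis for each co-primary endpoint. Starting from the primary imputation, "the imputed values for the rhNGF arm are shifted by a constant to represent a worse effect in each iteration". The grid is then fixed: "Assuming that the tipping point is between -10 and 0, the following actions will be performed", for shifts of 0, -0.1, -0.2 and so on to -10. The p-values are plotted, and "based on the plot, the approximate value of the tipping point" is read off against the 0.025 threshold. After that, "finest research of the tipping point will be performed in the range" of one unit either side of this value, in steps of 0.01.

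The same numbers serve Schirmer I (mm of wetting) and the SANDE global score (0 to 100 mm, SAP 12.2). The SAP gives no derivation of the limit of 10, no rule to extend the grid, and no instruction for a p-value still below 0.025 at the end of it. Protocol 9.4.3.2 defines the tipping points as the smallest shifts at which significance is lost and sets no range.

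The planning figures are in SAP section 5: "15 points in Global SANDE score improvement at Week 12, with a standard deviation of 20 points", "randomization ratio 1:1", "a total sample size of 90 evaluable patients (100 pts considering 10% of patients not evaluable after enrollment", and "considering a one-sided alpha of 0.025".

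**The concern.** A tipping-point analysis should show how unfavourable the unobserved outcomes must be before the conclusion changes. The shift applies only to imputed patients in one arm, so its effect on the treatment difference is the shift multiplied by the imputed fraction. With few imputed patients, a useful search needs large individual shifts.

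Ten units mean very different things on the two endpoints. For Schirmer, where response means more than 10 mm, a 10 mm reduction makes a non-responder of any imputed value up to 20 mm. For SANDE, 10 mm is half the planning SD and two-thirds of the planned difference, applied to a small part of one arm.

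SANDE must succeed for superiority to be claimed. A p-value plot that stays below 0.025 to the end of the grid could be presented as robustness although the search moved the treatment difference very little.

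**Working it through.** **Inputs.** From SAP section 5: difference 15, SD 20, 1:1 allocation, one-sided alpha 0.025, 90 evaluable of 100 enrolled (45 and 50 per arm), 10% not evaluable. From SAP 10.1.3: maximum shift 10. *Assumption:* the imputed fraction f of the cenegermin arm equals the 10% not-evaluable rate. The documents do not forecast f directly.

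**1. Reproduce the plan's figure.** With 45 per arm, a noncentral t calculation (88 df) gives SANDE power of 94.0%, as the SAP states.

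**2. Significance boundary.** With 50 per arm, SE = 20 × √(2/50) = 4.0. The boundary is 1.984 × 4.0 = 7.94 mm. An observed 15 has 15 − 7.94 = 7.06 mm to spare.

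**3. What the present grid does.** A shift D on a fraction f lowers the difference by f × D: 0.10 × 10 = 1.0 mm. It also adds about f(1 − f)D² to that arm's variance: 0.09 × 100 = 9. SE becomes √((800 + 9)/50) = 4.02. An estimate tips if it lies between 7.94 and about 1.0 + 1.984 × 4.02 = 8.98 mm. If the true difference is 15, that has probability 0.0275. Divided by the 0.961 probability of significance, it is 2.9% of significant trials.

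**4. Shift needed to overturn an observed 15.** Solve 15 − fD = 1.984 × √((800 + f(1 − f)D²)/50):

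| Imputed fraction | Shift per imputed patient | Difference left | Boundary at that shift |
|---|---|---|---|
| 5% | about 100 mm | 10.0 | 10.0 |
| 10% | about 57 mm | 9.3 | 9.3 |
| 15% | about 41 mm | 8.9 | 8.9 |

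These values are not capped at the ends of the scale.

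**5. Simulation.** 50 per arm, SD 20, 50 imputations, Rubin's rules, 1,500 trials per scenario, 10% missing in the vehicle arm, worsening direction, no cap. The 20% and 30% rates and the true effect of 10 are assumptions. Share of significant trials that tip within 10 mm:

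| True effect | Missing, cenegermin | Own-arm imputation | Copy Reference |
|---|---|---|---|
| 15 | 10% | 3% | 7% |
| 15 | 20% | 11% | 24% |
| 15 | 30% | 19% | 64% |
| 10 | 10% | 13% | 22% |
| 10 | 20% | 29% | 51% |
| 10 | 30% | 43% | 88% |

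In the first row with own-arm imputation, a longer grid tips 18% at 30 mm, 41% at 50 mm, 74% at 75 mm and 94% at 100 mm.

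**Limits.** Data are missing completely at random, there are no covariate or site terms, and SD 20 is taken as the residual SD; a smaller ANCOVA residual SD would make tipping rarer. MI-RD itself was not simulated, because its result depends on how treatment discontinuers fare.

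**The case against.** The strongest reply is that a bounded search still informs. With a worsening shift, survival to 10 mm is a true statement about a departure of half an SD, and it is applied to values already imputed from treatment discontinuers or from vehicle patients. The documents give no minimal important difference by which 10 mm could be called trivial. If few values are imputed, failure to tip is partly genuine robustness. The analysis is run only after success, leaves the primary test and type I error untouched, and stands beside MAR imputation, complete-case and per-protocol analyses. All of this stands. It limits the seriousness of the point but does not supply a suitable range or a rule for when nothing tips.

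Three stronger readings are tempting, and the documents do not support them.

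- *The check cannot give an answer, or almost no significant result could tip.* Borderline results do tip (one-sided p of about 0.014 to 0.025 at 10% imputed). The share rises with a smaller effect, more missing data or Copy Reference.
- *An observed 15 needs shifts of 71, 47 or 141 mm at 10%, 15% or 5% imputed, so at 5% no shift within the scale could suffice.* These come from dividing 7.06 by f with the SE held at 4.0. The shift inflates the variance, and the values fall to about 57, 41 and 100 mm.
- *The grid is too short whichever sign is used.* SAP Table 3 defines change as post-baseline minus baseline, so a negative shift improves SANDE and cannot tip at any length. SAP 10.1.1 speaks of a reduction, so a negative shift worsens it. That is a separate question of direction, to be reconciled separately.

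It is also fair to say that the 10% is a pooled not-evaluable rate, not a forecast of imputed week-12 SANDE values under cenegermin. Patients who stop treatment are asked to remain under observation, so the imputed fraction could be lower.

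**Conclusion.** The point holds as a gap in the specification of a sensitivity analysis. On the plan's own figures, with 10% of the cenegermin arm imputed and a worsening shift, the grid moves the SANDE difference by about 1 mm and finds a tipping point in about 3% of significant trials, or about 7% under Copy Reference. An observed 15-point difference lies far outside its reach: about 57 mm is needed at 10% imputed.

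Outside those base assumptions the share is higher, roughly 7% to 64% when the imputation base, the true effect or the missing fraction departs from them, and up to 88% when a smaller effect, 30% missing data and Copy Reference coincide. The likely outcome under the planning assumptions is therefore a weak bounded statement, with a refinement step that has no starting value and no rule for reporting it. This should be corrected before unblinding; it does not threaten the primary analysis.

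**What to change.** In SAP 10.1.3, give SANDE its own grid:

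- Shift imputed cenegermin scores in the unfavourable direction (higher score, that is, smaller reduction) from 0 until p ≥ 0.025 or the 100 mm scale limit is reached, for example in 1 mm steps and then 0.1 mm near the tipping point.
- Cap shifted scores at 0 and 100. Capping makes tipping rarer than the uncapped figures above.
- If nothing tips, omit the refined search and report *no tipping point within the scale*. That result would mean that even the worst possible scores for the imputed patients leave superiority standing.
- Keep the 10 mm grid for Schirmer.
- Reconcile the sign of the SANDE shift between Table 3 and 10.1.1 as a separate correction.

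The cost is a short SAP edit and a change of loop limits in planned code. A full coarse search from 0 to 100 in 1 mm steps has 101 points, the same as 0 to 10 in steps of 0.1. A fine search of 1 mm either side in 0.1 mm steps has 21 points, against 201 now.

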10.1.4 Supportive analyses

For each primary endpoint, the regression models detailed in section 10.1.2 will be performed for supportive purposes:

- by considering complete cases only (i.e. without considering patients with missing primary endpoint).
- on the PP set instead of FAS.

10.2 Analysis of secondary efficacy endpoints

10.2.1 Testing strategy and multiplicity adjustment

In case the analysis of the primary endpoints leads to rejection of null hypothesis, the following key secondary endpoints will be tested in a conditional sequential manner to show superiority of cenergermin versus control (at alpha one-sided 0.025) according to the following ranking:

1. Proportion of patients reaching a value of Schirmer I test (without anesthesia) >10mm/5min at week 8.
2. Change from baseline in SANDE scores for severity at week 12.
3. Change from baseline in SANDE scores for frequency at week 12.
4. Change from baseline in IDEEL modules (Quality of Life [27 questions], Dry eye Treatment satisfaction & Bother [10 questions], and Dry eye Symptom bother [20 questions]) at week 12 and at week 4 (in this order).
5. Change from baseline in Cornea and conjunctiva vital staining with fluorescein NEI scale at week 4, week 8 and at week 12 (in this order).
6. Change from baseline in TFBUT at week 4, week 8 and at week 12 (in this order).

This hierarchical test strategy protects the family-wise false positive error rate at the overall one-sided 0.025 level.

10.2.2 Analysis details

Analysis of key secondary endpoints are detailed below in sections 10.2.2.1 - 10.2.2.6 and p-values to be evaluated for comparison between treatments in a sequential order are the following:

1. P-value of treatment variable from logistic regression model on proportion of patients reaching a value of Schirmer I test (without anesthesia) >10mm/5min at week 8 (section 10.2.2.1),
2. P-value of treatment variable from ANCOVA regression model on change from baseline in SANDE score for severity at week 12 (section 10.2.2.2),
3. P-value of treatment variable from ANCOVA regression model on change from baseline in SANDE score for frequency at week 12 (section 10.2.2.3),
- 4.1 P-value of treatment variable from MMRM regression model on IDEEL Quality of Life module at week 12 (section 10.2.2.4),
- 4.2 P-value of treatment variable from MMRM regression model on IDEEL Dry eye Treatment satisfaction & Bother module at week 12 (section 10.2.2.4),
- 4.3 P-value of treatment variable from MMRM regression model on IDEEL Dry eye Symptom bother module at week 12 (section 10.2.2.4),

- 4.4 P-value of treatment variable from MMRM regression model on IDEEL Quality of Life module at week 4 (section 10.2.2.4),
- 4.5 P-value of treatment variable from MMRM regression model on IDEEL Dry eye Treatment satisfaction & Bother module at week 4 (section 10.2.2.4),
- 4.6 P-value of treatment variable from MMRM regression model on IDEEL Dry eye Symptom bother module at week 4 (section 10.2.2.4),
- 5.1 P-value of treatment variable from MMRM regression model on Change from baseline in Cornea and conjunctiva vital staining with fluorescein NEI scale at week 4 (section 10.2.2.5),
- 5.2 P-value of treatment variable from MMRM regression model on Change from baseline in Cornea and conjunctiva vital staining with fluorescein NEI scale at week 8 (section 10.2.2.5),
- 5.3 P-value of treatment variable from MMRM regression model on Change from baseline in Cornea and conjunctiva vital staining with fluorescein NEI scale at week 12 (section 10.2.2.5),
- 6.1 P-value of treatment variable from MMRM regression model on Change from baseline in TFBUT values at week 4 (section 10.2.2.6),
- 6.2 P-value of treatment variable from MMRM regression model on Change from baseline in TFBUT values at week 8 (section 10.2.2.6),
- 6.3 P-value of treatment variable from MMRM regression model on Change from baseline in TFBUT values at week 12 (section 10.2.2.6).

10.2.2.1 Schirmer I test >10mm/5min at week 8

The proportion of patients reaching a value of Schirmer I test (without anesthesia) >10mm/5min at week 8 will be analyzed as described in section 10.1.2.1 for the primary efficacy endpoints.

10.2.2.2 Change from baseline in SANDE score for severity at week 12

The change from baseline in SANDE score for severity at week 12 will be analyzed as described in section 10.1.2.2 for the primary efficacy endpoints.

10.2.2.3 Change from baseline in SANDE scores for frequency at week 12

The change from baseline in SANDE score for frequency at week 12 will be analyzed as described in section 10.1.2.2 for the primary efficacy endpoints.

10.2.2.4 Change from baseline in IDEEL modules (Quality of Life, Dry eye Treatment satisfaction & Bother, and Dry eye Symptom bother) at week 12 and at week 4

Rules for derivation of IDEEL scores are reported in section 12.3. The change from baseline of each IDEEL module will be analyzed by means of an MMRM adjusting by pre-defined factors (gender, age class, IDEEL module baseline value, treatment, visit, and treatment by visit interaction; subject will be considered as a random effect). The covariance matrix used will be "unstructured". Comparisons versus vehicle TID will be provided using least square means at each visit and overall and a one-sided test will be used to test for differences between treatment groups.

For the imputation of missing data, a regression model will be created by including the baseline value, gender, age class, and intermediate scores up to week 12. Two hundred data sets will be

generated, and the random seed number will be 225670. MI will be implemented in the following steps:

1. Partial imputation assuming MAR will be carried out to impute intermittent (non-monotone) missing data of IDEEL module score based on a multivariate joint Gaussian imputation model using the MCMC method. A separate imputation model will be used for each treatment arm. In case of non-convergence or non-estimability issues, a single imputation model will be considered (with treatment arm added as explanatory variable to the model). A total of 200 datasets will be created. These datasets will be utilized in Step #2.
2. The remaining monotone missing data will be imputed using a MI regression including the same explanatory variables of the previous step. According to MI-RD approach, only non-missing values from retrieve dropouts will be used to inform the regression model.
3. Each of the 200 imputed datasets will be analyzed using observed and imputed data. Rubin's rule will be used for combining results to draw inference.

If there are not enough retrieved dropouts for convergence of MI-RD regression model, a Copy Reference approach will be adopted to consider a MNAR mechanism for missing data. The final decision on the use of the MI-RD vs Copy-Reference for this endpoint will be done at the time of the analysis and reported in the CSR.

Whether for MI-RD or Copy-Reference approach, the adjusted estimated treatment differences in means for IDEEL module scores between cenegeimin and vehicle at each available timepoint will be displayed together with the corresponding two-side 95% confidence intervals and p-value.

10.2.2.5 Change from baseline in Cornea and conjunctiva vital staining with fluorescein NEI scale at week 4, week 8 and at week 12

Rules for derivation of NEI scores are reported in section 12.4. The change from baseline in Cornea and conjunctiva vital staining with fluorescein NEI scale will be analyzed by means of an MMRM adjusting by pre-defined factors (gender, age class, NEI scale baseline value, treatment, visit, and treatment by visit interaction; subject will be considered as a random effect). The covariance matrix used will be "unstructured". Comparisons versus vehicle TID will be provided using least square means at each visit and overall and a one-sided test will be used to test for differences between treatment groups.

For the imputation of missing data, a regression model will be created by including the baseline value, gender, age class, and intermediate scores up to week 12. Two hundred data sets will be generated, and the random seed number will be 240550. MI will be implemented in the following steps:

1. Partial imputation assuming MAR will be carried out to impute intermittent (non-monotone) missing data of NEI scale score based on a multivariate joint Gaussian imputation model using the MCMC method. A separate imputation model will be used for each treatment arm. In case of non-convergence or non-estimability issues, a single imputation model will be considered (with treatment arm added as explanatory variable to the model). A total of 200 datasets will be created. These datasets will be utilized in Step #2.
2. The remaining monotone missing data will be imputed using a MI regression including the same explanatory variables of the previous step. According to MI-RD approach, only non-missing values from retrieve dropouts will be used to inform the regression model.
3. Each of the 200 imputed datasets will be analyzed using observed and imputed data. Rubin's rule will be used for combining results to draw inference.

If there are not enough retrieved dropouts for convergence of MI-RD regression model, a Copy Reference approach will be adopted to consider a MNAR mechanism for missing data. The final decision on the use of the MI-RD vs Copy-Reference for this endpoint will be done at the time of the analysis and reported in the CSR.

Whether for MI-RD or Copy-Reference approach, the adjusted estimated treatment differences in means for NEI scale scores between cenegeamin and vehicle at each available timepoint will be displayed together with the corresponding two-side 95% confidence intervals and p-value.

10.2.2.6 Change from baseline in TFBUT at week 4, week 8 and at week 12

The change from baseline in TFBUT values will be analyzed by means of a MMRM adjusting by pre-defined factors (gender, age class, TFBUT baseline value, treatment, visit, and treatment by visit interaction; subject will be considered as a random effect). The covariance matrix used will be "unstructured". Comparisons versus vehicle TID will be provided using least square means at each visit and overall and a one-sided test will be used to test for differences between treatment groups.

For the imputation of missing data, a regression model will be created by including the baseline value, gender, age class, and intermediate scores up to week 12. Two hundred data sets will be generated, and the random seed number will be 101149. MI will be implemented in the following steps:

1. Partial imputation assuming MAR will be carried out to impute intermittent (non-monotone) missing data of TFBUT values based on a multivariate joint Gaussian imputation model using the MCMC method. A separate imputation model will be used for each treatment arm. In case of non-convergence or non-estimability issues, a single imputation model will be considered (with treatment arm added as explanatory variable to the model). A total of 200 datasets will be created. These datasets will be utilized in Step #2.
2. The remaining monotone missing data will be imputed using a MI regression including the same explanatory variables of the previous step. According to MI-RD approach, only non-missing values from retrieve dropouts will be used to inform the regression model.
3. Each of the 200 imputed datasets will be analyzed using observed and imputed data. Rubin's rule will be used for combining results to draw inference.

If there are not enough retrieved dropouts for convergence of MI-RD regression model, a Copy Reference approach will be adopted to consider a MNAR mechanism for missing data. The final decision on the use of the MI-RD vs Copy-Reference for this endpoint will be done at the time of the analysis and reported in the CSR.

Whether for MI-RD or Copy-Reference approach, the adjusted estimated treatment differences in means for NEI scale scores between cenegeamin and vehicle at each available timepoint will be displayed together with the corresponding two-side 95% confidence intervals and p-value.

